Risk of Injury and Discomfort: Transcranial magnetic stimulation has been cleared for use in the USA by the FDA. TMS (the methodology used in this experiment) has nothing to do with electroconvulsive therapy that applies many orders of magnitude higher stimulation current. The level of electrical stimulation produced by TMS is within the range of activity that is endogenous to the brain. Furthermore, the intensity of stimulation is calibrated to the sensitivity of the individual participant such that the level of stimulation is matched to that of naturally occurring activity. In order to monitor side-effects, we will be administering an adverse effects stimulation questionnaire after each stimulation session to determine whether these effects were experienced. Research personnel present during these sessions will also check with the participant periodically during the stimulation to see whether they are comfortable. If any side-effect occurs that is rated by the participant and confirmed by the researcher to be stronger than "moderate," the stimulation will be immediately stopped.

Risk of Psychological Discomfort: There is a psychological element in that some participants may become claustrophobic upon entering the small space of the MRI bore. To reduce psychological distress, participants are informed that they can withdraw consent and stop participation at any time. Participants are monitored throughout the MRI scans and can terminate the scan at any time by squeezing a ball held in the hand, and will be quickly removed from the MRI bore. There is additionally a risk of psychological discomfort from receiving transcranial magnetic stimulation (TMS). Due to the discomfort from receiving TMS and the proximity of the TMS coil to the face and head of the participant, this can result in psychological discomfort. Similar to MRI, participants are informed that they can withdraw consent and stop participation at any time. Participants are monitored throughout the TMS sessions and can stop receiving stimulation at any time by physically moving away from the TMS coil. The field of stimulation is less than a couple centimeters. Furthermore, researchers monitor the participant throughout stimulation and will check in with the participant approximately every 5 minutes between each task block.

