The order of regions (dlPFC then mPFC, or mPFC then dlPFC) targeted by TMS in the third and fourth session will be randomized and counter-balanced. First, the participants will be fitted with a low-profile EEG net and EMG electrodes to the hand and forearm. For the third and fourth session, the same stimulator intensity will be used as in the first session. The structural MRI and regions of interest (dlPFC and mPFC) are imported into Localite neuronavigation software. The participant wears a 3D stereotaxic tracking headband and is registered to their structural MRI. Then, the TMS coil is targeted to either mPFC or dlPFC and the position of the coil relative to the head is recorded throughout the session. The participant performs the S-EEfRT as the patterned trains of TMS are delivered on every trial. Each block of the study is randomized to receive either delta-beta patterned (triplets of TMS pulses at 20 Hz every 3Hz), theta-gamma patterned (triplets of pulses at 50 Hz every 5 Hz), or an arrhythmic pattern (same number of pulses and duration with a random inter-pulse interval). After stimulation, a questionnaire is provided with common side effects of TMS. Based on the results of the stimulation side effects questionnaire, a structured adverse events interview is conducted to acquire more information regarding any side effects that were selected to be “very high” by the participant. This session will take approximately 2 hours.

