4.2 SCIENTIFIC RATIONALE FOR STUDY DESIGN

This study is a fully crossed target engagement study. It is not possible to include blinding in the study for either the participant or the experimenter. The difference between the active control pattern of TMS and the targeted pattern of TMS as well as the difference between dorsolateral PFC and medial PFC will not be meaningfully discernible to the participant as there is a difference of only a few centimeters between sites and only a fraction of a second for the stimulation patterns. There is no obvious association between the site of stimulation and the frequency of stimulation and the task itself. Therefore, not only is blinding

not possible, but it is not necessary for the scientific questions under investigation in this study. In a recent review by Duecker and Sack *Frontiers in Psychology* 2015, the authors survey modern approaches to creating a sham form of TMS. These efforts have been unsuccessful despite increasingly sophisticated designs. The authors found that even with moderate success in blinding in a parallel arm study where the participant is naïve to stimulation, when a design is crossover, the participants become aware that the stimulation is placebo. These observations lead to the conclusion that even when sham stimulation is used, the experiment should include an active control condition such as an alternate location of stimulation or an alternate frequency of stimulation: “TMS experiments always require an active TMS control condition, and sham TMS approaches can never be sufficient as they fail to demonstrate such specificity” (Duecker and Sack 2015).

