stimulator output until a motor evoked potential (MEP) is generated: defined as a near-instantaneous increase muscle activity greater than 200 microvolts. Next, the intensity of single pulse TMS will be lowered until a MEP is generated on five out of ten pulses. This is defined as the motor threshold for the participant (Rossi et al. 2009). If the motor threshold cannot be determined via MEP, the experimenter will use visible twitches instead of MEP. Participants will receive 15 pulses of patterned TMS at 80% of their motor threshold during every trial. Patterned TMS takes three different forms (Figure 2). Delta-beta TMS delivers bursts of three pulses at 20 Hz (50 millisecond inter-pulse interval) with an inter-burst interval of 3 Hz (167 milliseconds). Theta-gamma TMS delivers bursts of three pulses at 50 Hz (20 millisecond inter-pulse interval) with an inter-burst interval of 5 Hz (200 milliseconds). As a control for the frequency-specificity of patterned TMS, arrhythmic TMS is delivered with a randomized inter-pulse intervals that are generated for each trial. The duration of arrhythmic TMS is randomly selected from a uniform distribution between the duration of delta-beta and theta-gamma TMS. The minimum inter-pulse interval will be 20 milliseconds. Between every train will be at least 11 seconds. An inter-train-interval of 11 seconds or greater allows for any residual effects of stimulation to return to baseline. This intensity, inter-pulse-interval, and inter-train-interval is well within the safety guidelines set forth for repetitive TMS (Wassermann, 1998; Rossi et al., 2009) and has been used in similar paradigms as the one described here. For example, Hermiller et al. 2020 delivered two seconds of theta-gamma patterned TMS (30 pulses per trial) at 80% of motor threshold (Hermiller et al. 2020). In addition, many other studies have delivered trains of TMS at higher intensities, upwards of 120% of motor threshold, on every trial of a cognitive task (Thut et al. 2011; Hanslmayr et al. 2014; Albouy et al. 2017)(Riddle et al. 2019; Riddle et al. 2020c; Sauseng et al. 2009). During a TMS session, participants will complete six blocks of 30 trials each. The participant will receive stimulation in either delta-beta, theta-gamma, or arrhythmic in a blocked design (the same stimulation is delivered for every trial in a block). The sequence of blocks will be randomized and counterbalanced such that each participant received each condition of TMS for 60 trials total. The third and fourth session of the experiment will be both be TMS sessions, where TMS is delivered to either the dorsolateral prefrontal cortex (dlPFC) or to medial prefrontal cortex (mPFC). The order and TMS sites will be randomized and counterbalanced across participants. Thus, at completion of the full experiment, participants will have received 12 blocks of 30 trials each of stimulation (180 trials per TMS session). In addition, two abbreviated blocks of TMS to mPFC and dlPFC will be administered at the end of the first session to assess for tolerability of TMS.

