8.2 SAFETY AND OTHER ASSESSMENTS

1. A stimulation side effects questionnaire will be administered at the end of each stimulation session. This tool will be used as a safety measure and to collect data on the experience of the participant. The side effects questionnaire was adapted from studies in our group that used a different form of stimulation (transcranial electric stimulation), and was updated to remove questions that are not relevant to transcranial magnetic stimulation.
2. An MRI screening form will be administered over the phone during the phone screening and within 24 hours prior to the MRI session. This screening form is the standard provided by the Brain Research Imaging Center (BRIC) at UNC. During the phone screening, if there is any ambiguity in the eligibility of the participant, then we consult with the technicians at the BRIC for approval to conduct an MRI. Then, in the 24 hours prior to their MRI session, MR technicians at the center review a new screening form and confirm their eligibility to receive an MRI. Because this is the same form used in the screening for the experiment, the only way that a participant would fail to be eligible at this stage is if there was some change in their eligibility between sessions. While this is highly unlikely, the participant would be discontinued from participating.
3. A TMS screening form will be administered over the phone and at the start of each of the TMS session. If there is any ambiguity in the contraindications for the TMS form, then the medical monitor, [name], who is an epileptologist is consulted and final approval is acquired. Similar to the MRI screening form, it is highly unlikely that eligibility will change between sessions. Out of an excess of caution, we administer the TMS screening form at each TMS session to confirm that there is no contraindication, otherwise participation is discontinued.

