9.4.5 SAFETY ANALYSES

The stimulation questionnaire will be administered for the third and fourth session after stimulation. This questionnaire solicits ratings of 10 possible adverse effects associated with non-invasive brain stimulation, on a scale of 0 (absent), 1 (low), 2 (medium), 3 (high), 4 (very high). The side effects include that are expected to occur in some participants are headache, neck pain, scalp pain, muscle stiffness, skin tingling, skin itching, ringing noise, trouble concentrating, improved mood, and dizziness. Paired t-tests with random effect "participant" will be calculated per adverse effect to determine if there are any differences in adverse effect severity between sessions (delta-beta TMS, theta-gamma TMS, and arrhythmic TMS to dlPFC versus mPFC). Subjective severity per adverse effect will be described with mean and standard deviation. In addition, we will analyze the severity of each adverse event as determined by the Medical Monitor and PI. The process for determining the severity of an adverse event is detailed in Section 2.3.4.

A linear model with random effect "participant" will be calculated per adverse effect to determine if there are any differences in adverse effect severity between sessions (dlPFC and mPFC as categorical independent variables) and adverse effect severity as the continuous dependent variable. Subjective severity per adverse effect will be described with mean and standard deviation. In addition, we will analyze the severity of each adverse event as determined by the Medical Monitor and PI.

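### Side effects are rated once per session, after all three patterns have been mixed, so the planned data can compare them by site but never by stimulation pattern

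*Combined protocol and SAP*

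**What the plan says.** **When side effects are rated.** Section 8.2: "A stimulation side effects questionnaire will be administered at the end of each stimulation session". Section 9.4.5: "The stimulation questionnaire will be administered for the third and fourth session after stimulation". Section 4.1 agrees: "After stimulation, a questionnaire is provided with common side effects of TMS". The schedule of activities (1.3) shows one questionnaire entry per session. On content, "This questionnaire solicits ratings of 10 possible adverse effects", each scored 0 to 4. None of the items listed in 9.4.5 asks whether the patterns felt different.

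**What a session contains.** Section 4.3: "During a TMS session, participants will complete six blocks of 30 trials each", with 60 trials of each pattern. Section 6.3 requires all three patterns in the first three blocks and again in the last three, with no immediate repeat. By design, Sessions 3 and 4 differ in stimulation site.

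**What is to be compared.** The first paragraph of 9.4.5 plans paired t-tests per adverse effect on "differences in adverse effect severity between sessions (delta-beta TMS, theta-gamma TMS, and arrhythmic TMS to dlPFC versus mPFC". The second plans a linear model in which site is the only factor.

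**Why it bears on blinding.** Section 4.2 says that the difference between patterns, and between sites, "will not be meaningfully discernible to the participant", and goes on to call blinding unnecessary.

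**The concern.** Pattern is the factor varied within each session, and 9.4.2 interprets only differences from arrhythmic TMS. The primary outcome is a voluntary choice between a hard and an easy task, which discomfort or distraction could plausibly move. If one pattern were more unpleasant than another, a reader would want to know before attributing a change in hard choices to goal-directed behavior.

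The patterns do differ physically. Section 4.3 gives within-burst rates of 20 Hz and 50 Hz, and trains of different length. The plan asserts that participants cannot meaningfully tell them apart, and collects nothing by pattern that would test this.

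**Working it through.** **1. The plan's trial counts.** 6 blocks x 30 trials = 180 trials per session; 2 blocks x 30 = 60 trials per pattern. Both agree with 4.3.

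**2. Allowed block orders.** Each half-session is one of 3! = 6 orders, so there are 6 x 6 = 36 pairs. The no-repeat rule removes those in which block 4 repeats block 3. For each first half, 2 of the 6 second halves start with that pattern, so 6 x 2 = 12 are removed and 24 remain. All 24 contain exactly two blocks of each pattern.

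**3. What one session rating carries.** The share of each pattern is 60/180 = 1/3 in every session, for every participant, at either site.

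**4. Estimability with the planned ratings.** With 24 completers (9.2) there are 24 x 2 = 48 ratings per item. A model with 24 participant indicators, site and session order has rank 26. Adding two pattern terms and two pattern-by-site terms changes nothing: each pattern column is the constant 1/3, already in the span of the participant indicators, and each interaction column is one third of the site column. The rank stays at 26, a gain of 0.

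**5. Other sources of pattern-level information.**
- The check-ins in 2.3.1 (staff "will check in with the participant approximately every 5 minutes between each task block") have no specified rating or record.
- The structured adverse event interview (2.3.4) asks about onset and time course, but only after a rating of very high.
- The Session 1 tolerability test (4.1) has one short block per site, with no pattern stated.

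None supplies a systematic pattern comparison.

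**6. Where a difference in feel would enter the primary analysis.** Write DB, TG and AR for the effect of discomfort on hard choices under each pattern.
- Site-by-type interaction: [(DB - AR) - (TG - AR)] at dlPFC minus the same at mPFC = (DB - TG) at dlPFC - (DB - TG) at mPFC. AR drops out, and a DB-TG difference equal at both sites cancels. Only one that differs by site remains.
- Delta-beta minus arrhythmic at dlPFC, the direction stated in 9.2: DB - AR. Nothing cancels, even if the difference is the same at both sites.

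For scale only, 3 more easy choices in a 60-trial cell is 3/60 = 5 percentage points.

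**7. With one rating per block.** 6 x 2 = 12 ratings per participant, 12/6 = 2 per site-by-pattern cell, 288 per item over 24 completers. The same model now has rank 30: all four added terms become estimable.

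**8. Precision.** The noncentral-t calculation for a paired t-test reproduces the plan's figures in 9.2: d = 0.60 with n = 24 gives 80.4% (stated 80%), and d = 1.01 with n = 15 gives 95.3% (stated 95%). For a paired contrast of two patterns at two-sided 0.05, 24 completers give 80% power at 0.60 SD of the difference, or 0.70 SD with Bonferroni over the three pattern pairs. The 95% confidence interval half-width is t(0.975, 23)/sqrt(24) = 0.42 SD.

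**The case against.** Much of the case on the other side stands.

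- **The bracket in 9.4.5 need not promise an impossible test.** It can be read as two sessions, each holding all three patterns, compared by site. The second paragraph of 9.4.5 and the interim safety analysis in 9.4.7, which compares stimulation sites, both fit that reading. A pattern comparison is then simply not planned, and the wording still needs reconciling.
- **The defence of no blinding does not rest on feel alone.** Sections 4.2 and 6.3 also cite infeasibility, active controls, randomized blocks not known until they start, a computerized task, little interaction and hypotheses not explained to participants. Noticing that two patterns feel different does not tell a participant which should raise hard choices.
- **Some features are matched or masked.** Every trial has 15 pulses at the same intensity, arrhythmic train length is drawn from between the two rhythmic lengths, and sealed ear-buds play white noise (4.3). That the patterns are audible to the experimenter says little about the participant. Masking reduces the difference but does not verify its absence.
- **Bias is hypothetical.** Stimulation precedes every decision, so choosing the easy task does not avoid it, and nothing in the documents shows that discomfort differs by pattern.

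A reader might also infer that the trial leaves untested the statement in 4.3 that delta-beta is probably the safer pattern. That statement concerns seizure risk judged by inter-pulse interval. Neither the questionnaire nor block-level discomfort ratings would address it.

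**Conclusion.** The point holds as one of estimability: with one rating per session, pattern and pattern-by-site contrasts in side effects cannot be estimated at any sample size, on either reading of 9.4.5. The site contrast, on 24 pairs, can. This follows from the block rule and the questionnaire timing and needs no assumed effect.

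The consequence is limited. The plan cannot check that arrhythmic TMS felt like the patterns it is subtracted from. By step 6 this matters most for the delta-beta minus arrhythmic contrast at dlPFC, and less for the interaction. A reader might conclude that the primary result is biased or that the case for running unblinded fails. The documents support neither: they give no discomfort effect, indiscernibility is one support among several, and the 5-point figure is illustration. The primary analysis can still be run.

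The precision figures assume 24 completers with complete ratings, approximate normality of the paired differences, and two-sided testing, which 9.4.1 does not state.

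**What to change.** 1. **Collect.** At the five existing between-block check-ins in each TMS session, and once after block 6 before the questionnaire, record a 0-4 rating of discomfort and one of distraction with the block's pattern code. The check-ins alone give 5 x 2 = 10 occasions; the extra rating after block 6 is needed to reach 12, or 2 per cell.
2. **Analyse.** In 9.4.5, model these ratings by pattern, site and pattern-by-site, with participant as a random effect, and report estimates with confidence intervals.
3. **Reconcile.** Merge the two paragraphs of 9.4.5 into one analysis and state that the end-of-session questionnaire compares sites only.
4. **Interpret, do not adjust.** Use the ratings to help read the primary result. They should not be a covariate in the primary ANOVA: they are taken after stimulation and may be affected by the pattern, and a block-level covariate does not fit an analysis of four difference scores per participant.

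Cost: a few seconds per block and two extra fields on the case report form. Repeated questions may draw some attention to sensations, though equally after every pattern. Pattern-level ratings cannot be recovered for sessions already completed. If block ratings are not adopted, step 3 should still be done, and the report should say that similarity of feel between patterns was assumed.

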7. STUDY INTERVENTION DISCONTINUATION AND PARTICIPANT DISCONTINUATION/WITHDRAWAL

7.1 DISCONTINUATION OF STUDY INTERVENTION

Discontinuation of stimulation during session 3 or session 4 means that study participation is halted and no other sessions are completed. If a clinically significant finding is identified after enrollment, the investigator or qualified designee will determine if any change in participant management is needed. Any new clinically relevant finding will be reported as an adverse event (AE).

The study intervention (i.e., patterned transcranial magnetic stimulation) will be discontinued for the following reasons:

- Any clinical adverse event (AE), laboratory abnormality, intercurrent illness or other medical condition, or situation occurs such that continued participation in the study would not be in the best interest of the participant.
- The participant meets any exclusion criteria (either newly developed or not previously recognized).

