7.3 LOST TO FOLLOW-UP

A participant will be considered lost to follow-up if he or she fails to return for 1 scheduled visit and is unable to be contacted by the study site staff. All efforts will be made to ensure participants are not lost

to follow-up, including developing rapport and ensuring enrolled participants are reminded of their session dates. Research personnel will be flexible in timing, including offering this session later in the day as well as some weekends.

Every effort will be made to contact participants who are lost to follow-up, including contacting via email and phone. However, if a participant is lost to follow-up, the missed session will be labeled as missing data and our pre-determined analysis plan takes into consideration missing data. Of note, we will continue data collection until the specified number of participants complete the full study. Thus, the statistical analysis plan will not be impacted by those participants that are lost to follow-up.

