9.2 SAMPLE SIZE DETERMINATION

The sample size is 24 participants in the final dataset to be used in analysis. However, to ensure that 24 participants complete the experiment, we conservatively estimate to enroll 50 participants as a ceiling for the sake of IRB approval. The motivation for the sample size of 24 participants in the analysis is explained below. The sample size is determined based on previous experiments from our group: the effect size of previous findings and the reliability of our estimates. Our estimators are precise due to sufficient number of trials per condition with each participant and that the tasks are titrated to the individual.

Primary outcome: Rhythmic TMS to lateral frontal cortex at delta-beta frequency will increase goal-directed behavior relative to arrhythmic TMS.

Previous Data: The planning and refinement of the proposed study was informed by our previous experiments that serve as preliminary data for the proposal. In our previous experiment, we delivered rhythmic TMS to lateral frontal cortex to increase performance in a cognitive control task (Riddle et al. 2020b). In our previous study, there was a significant interaction between TMS site and TMS frequency in a two-way repeated-measures ANOVA such that the improvement in performance in the cognitive control task was site and frequency-specific. The effect size from the partial-eta square was 0.23, and the effect from a dependent t-test was 0.532, with 20 participants. The experimental design of this previous study is similar to the current study in that there are two sites for stimulation (lateral frontal and medial frontal) with two different stimulation frequencies (delta-beta and theta-gamma). Both studies used an arrhythmic condition to control for non-specific effects of TMS.

Sample Size Determination and Power Calculation: Based on this previous effect size, we estimated that our participant count at 24 participants is powered at >95%.

[figure not shown]

Figure 3. Power calculation for the interaction effect in two-way repeated-measures ANOVA modeled as within factors interaction in a two-way ANOVA with partial-eta square of 0.23, and a correlation between variables of 0.77 based on Riddle, Scimeca et al. 2021. Power calculation run using the G*Power software. Proposed number of participants is 24 and is depicted in red.

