9.3 POPULATIONS FOR ANALYSES

Every effort will be made to ensure all enrolled and randomized participants complete all study sessions as described in this protocol. For this study, enrolled eligible healthy participants will be randomized to receive stimulation to frontal and parietal cortex in a randomized sequence. If a participant completes session 4, then they will be included in all analyses moving forward.

As previously stated in **Section 7 Study Intervention Discontinuation and Participant Discontinuation/Withdrawal**, enrolled participants who do not get randomized will be replaced. If required, then we will create additional blocks of 10 randomized sequences. Therefore, we will collect data until 24 participants complete the study and are eligible for analysis.

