9.4 STATISTICAL ANALYSES

9.4.1 GENERAL APPROACH

All testing described below assumes a significance threshold of $p = 0.05$. Analyses will be deemed to be statistically significant if the p -value is less than this threshold. An analysis that does not exceed this threshold will be considered inconclusive. Continuous data will be described using means, standard deviations, and confidence intervals, while categorical data will be described using counts/percentages.

There may be additional covariates included in the analysis. Data will be assessed for normality and, if deemed necessary, corrective procedures will be applied (e.g., log normalization). Based on our previous dataset, we expect that the variables used here will be approximately Gaussian. However, if the distribution of a variable displays a skewed tail and a test for normality fails, then it is justified to use a corrective procedure. This correction will be applied upon consideration of the variables themselves, and not based on the result of the intended analysis.

Data will be collected until 24 participants complete the study and all data is usable. Given that recruitment will be feasible in a convenience sample, we expect to have complete data and all analyses will include the full participant pool. However, if there are technical errors that are not caught in time, then the affected analyses may have less participants. In this scenario, the data for a participant is then completely removed from the analysis.

The effects of stimulation are expected to be transitory, lasting for only a second or two after stimulation. For this reason, stimulation is delivered “online” immediately preceding the time at which the cognitive processes of interest are engaged. During each session, we include a control condition (arrhythmic TMS) that will be subtracted from the conditions of interest (delta-beta TMS and theta-gamma TMS). Therefore, we control for any effects of sequence or time within each session by subtracting each metric of interest from the condition-matched arrhythmic TMS metric. Furthermore, any learning effects from performing the reward-based decision-making task should be stabilized by the 3rd session. These methods are typical

in cognitive neuroscience paradigms. For the reasons listed above, it is unlikely that there will be any effect of sequence or carryover effects between sessions.

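### Section 9.4.5 summarises the ordered 0–4 side-effect ratings by mean and SD, with no count per level and no defined safety population

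*Combined protocol and SAP*

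**What the plan says.** Section 9.4.5 lists ten possible side effects, each rated from 0 (absent) to 4 (very high) after sessions 3 and 4. It states twice that "Subjective severity per adverse effect will be described with mean and standard deviation". It compares the sites by paired t-tests and by a linear model with a participant random effect, the latter taking "adverse effect severity as the continuous dependent variable". It adds that adverse events will be analysed by the severity that the medical monitor and principal investigator assign.

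The general rule in 9.4.1 is that "categorical data will be described using counts/percentages", while continuous data get means, SDs and confidence intervals.

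On who is analysed:

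- 9.2: "The sample size is 24 participants in the final dataset to be used in analysis".
- 9.3: "If a participant completes session 4, then they will be included in all analyses moving forward". No separate safety set is named.
- 9.4.1: "Data will be collected until 24 participants complete the study and all data is usable".
- 7.3: "the statistical analysis plan will not be impacted by those participants that are lost to follow-up".
- 7.1: "Discontinuation of stimulation during session 3 or session 4 means that study participation is halted and no other sessions are completed".

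Section 2.3.4 makes a questionnaire rating of very high the threshold for an adverse event. Section 7.2 promises that reasons for drop-out will be reported.

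**The concern.** There are two separate gaps.

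The first is the summary itself. A tolerability reader wants to know how many people had a headache or scalp pain, and how many had it badly. Mean and SD do not generally answer either question for a five-level scale. Because 9.4.5 treats the ratings as continuous, the counts rule in 9.4.1 does not secure a frequency table.

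The second is the denominator. Under 2.3.1, stimulation stops if a side effect is confirmed as worse than moderate, and under 7.1 stopping in session 3 or 4 ends participation. People with stronger reactions can therefore become non-completers. If the summary covers only the 24 completers, it may leave them out and look more favourable than the experience of everyone stimulated.

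What is at stake is the usefulness of the tolerability report for a novel stimulation pattern. The study has no safety objective.

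**Working it through.** The plan gives no rating distribution and no early-stop rate, so there is no stated figure to reproduce. The numbers below are worked examples, not probabilities.

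**Inputs.** 24 participants (9.2, 9.3); levels 0 to 4 (9.4.5). The number of early stops, 1 to 3, is assumed.

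**Step 1. Do mean and SD fix the counts?** Let c0 to c4 be the numbers at each level, with S = c1 + 2c2 + 3c3 + 4c4 and T = c1 + 4c2 + 9c3 + 16c4. Then mean = S/24 and SD = √[(T − S²/24)/23].

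Take S = 18 and T = 36. Mean = 18/24 = 0.75; SD = √[(36 − 13.5)/23] = √(22.5/23) = 0.989. Since T − S = 2c2 + 6c3 + 12c4 = 18, we need c2 + 3c3 + 6c4 = 9. There are six solutions:

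| c0 | c1 | c2 | c3 | c4 | Rating 3 or more | Any effect |
|---|---|---|---|---|---|---|
| 15 | 0 | 9 | 0 | 0 | 0 | 9 |
| 14 | 3 | 6 | 1 | 0 | 1 | 10 |
| 13 | 6 | 3 | 2 | 0 | 2 | 11 |
| 12 | 9 | 0 | 3 | 0 | 3 | 12 |
| 12 | 8 | 3 | 0 | 1 | 1 | 12 |
| 11 | 11 | 0 | 1 | 1 | 2 | 13 |

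No other pattern of 24 ratings rounds to mean 0.75 and SD 0.99.

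A second example is S = 12 and T = 24: mean 0.50, SD = √[(24 − 6)/23] = 0.885 (0.8847, so 0.88 to two decimals). Here c2 + 3c3 + 6c4 = 6, which gives (18,0,6,0,0), (17,3,3,1,0), (16,6,0,2,0) and (15,8,0,0,1). The number rating 3 or more is 0, 1 or 2, and the number with any effect runs from 6 to 9.

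**Step 2. Where the ambiguity ends.** A widespread strong reaction would still show: 12 ratings of 3 and 12 of 0 give a mean of 36/24 = 1.5.

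**Step 3. What counts would show.** The extremes in the first table separate directly (Clopper-Pearson):

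- 0/24 = 0%, 95% CI 0% to 14.2%.
- 3/24 = 12.5%, 95% CI 2.7% to 32.4%.

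**Step 4. Population.** If k people stimulated in session 3 do not complete session 4, and collection continues to 24 completers, a completer summary omits k/(24 + k) of those stimulated in session 3, whatever they rated:

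- k = 1: 1/25 = 4.0%
- k = 2: 2/26 = 7.7%
- k = 3: 3/27 = 11.1%

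**Step 5. The two planned comparisons.** The paired t-test can use only the 24 pairs (48 ratings). The random-effect model can also use single-session participants, so it has 48 + k = 49 to 51 ratings. With complete pairs they agree: in an illustrative set of 24 pairs both gave a contrast of 0.375 and a test statistic of 2.58.

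**The case against.** The best counter-argument is that strong reactions already have other routes into the report. Every rating of 4 is an adverse event under 2.3.4, and 9.4.5 plans to analyse adverse events by graded severity, which is categorical and so falls under the counts rule. That stands for ratings of 4, and knowing those would distinguish some of the patterns above. It does not resolve level 3: the four patterns at mean 0.75 with no rating of 4 still contain 0, 1, 2 or 3 people rating 3. Some of these might be recorded, because 8.3.1 sets no rating threshold, 8.3.4 captures all adverse events, and 6.1.2 mentions interviews for common side effects. Nothing assures it.

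On the population, 9.3 says who is included and excludes nobody. Section 7.3 calls only the missed session missing, and the random-effect model accepts a participant with one session. All of that is right, so the plan does not bar non-completers' ratings. But no text gives those ratings a place in the summary. The promised reason for drop-out is not a summary of ratings.

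The stopping rule in 2.3.1 should also bring some strong reactions to light as reported drop-outs. Its moderate threshold is not a level of the 0–4 scale, however, so which rating would lead to a stop is not stated. The tolerability blocks in session 1 (4.1) may well keep early stops few.

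Finally, mean and SD for a 0–4 rating is a common choice, and nothing prevents adding a table. That is fair, and it is why this is a small point.

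**Conclusion.** The concern holds as a minor reporting gap. As written, the plan need not state how many participants rated an effect 3 or more, or had it at all, and it does not assure that non-completers' ratings are summarised. In the worked examples the same mean and SD cover 0 to 3 of 24 participants rating 3 or more. A completers-only summary would omit 4.0% to 11.1% of those stimulated in session 3 if 1 to 3 people stop early. These sizes depend on chosen rating patterns and an assumed number of early stops; the documents supply neither. The primary and secondary results are unaffected.

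**What to change.** In 9.4.5, for each effect and session, report the number and percentage at each level 0 to 4, and the number and percentage rating 3 or more with an exact 95% CI. State that the denominator is everyone who received stimulation in that session, including those who do not complete session 4. Keep mean and SD as supplementary. If only one site comparison per effect is retained, keep the random-effect linear model and drop the paired t-test, since the model can use single-session participants.

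The cost is a few lines of SAP wording and one extra table from data already collected. The downsides are wide intervals at 24 participants and denominators that may differ between sessions.
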